12. STATISTICAL ANALYSIS

- *Describe how your data will be used to test the hypotheses.*
- *State clearly what variables will be tested and what statistical tests will be used.*

- *Include sample size calculations.*
- *If this is a pilot study, state which variables will be examined for hypothesis generation in later studies.*

Blinding:

Due to the nature of the intervention (bolus block, continuous infusion pump), it is not possible to blind the physicians or patients.

Consent:

Consent will be obtained during the preoperative visit, prior to surgery.

Randomization:

Subjects will be randomly assigned in a 1:1 ratio to either bolus block or continuous catheter. The randomization will be stratified by hospital (Plainview, Franklin, Huntington, Long Island Jewish, or North Shore University Hospital).

The Biostatistics Unit will develop a randomization procedure using a permuted block design within the Biostatistics Randomization Management System (BRMS).

Additional details of the procedure, including required record keeping, will be further developed upon approval of this protocol. The Biostatistics Unit has extensive experience in implementing and in producing detailed documentation for such procedures.

Intention to Treat (ITT):

All analyses will be carried out according to the ITT principle. The ITT population will be all subjects randomized, regardless of what treatment they actually received. All patients will be analyzed in the group to which they were randomized.

Statistical Considerations:**Specific Aims:**

To compare the efficacy of two postoperative pain control methods (bolus block, continuous catheter) in patients undergoing ACL reconstruction.

Primary Outcome

Outcomes measured on post-operative days 0, 1,2,3,4,7, and at the post-operative follow-up visit. (Outcomes for days 0, 1,2,3,4, and 7 will be obtained via email and electronic surveys . Outcomes for the post-operative follow-up visit will be measured during the postoperative visit which takes place between days 10 and 14. This will be referred to as "Day 10").

- Pain Control

- Maximum pain will be measured on a scale of 0 to 10, where 0 represents no pain and 10 represents the worst possible pain. Patients will report the maximum pain felt in the 24 hours
- Current pain will be measured on a scale of 0 to 10, where 0 represents no pain and 10 represents the worst possible pain.
- Daily opioid consumption (expressed as morphine equivalents).

Secondary Outcomes

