Outcomes measured on post-operative days 1,2,3,4,7, and at the post-operative follow-up visit.

- Quality of Sleep
 - Trouble falling asleep due to pain (yes,no)
 - Wake due to pain (yes,no)

Outcomes measured at post-operative follow-up visit

- Satisfaction with surgery, on a scale of 0 to 10, where 0 represents extremely dissatisfied and 10 extremely satisfied
- Adverse events: Adverse events will be assessed at each visit. At the end of the study, each subject will be categorized as having had one or more adverse events, or not having had any adverse events.
- Serious Adverse events: Serious adverse events will be assessed at each visit and via telephone on post-operative day 1, 2, 3, 4 and 7. At the end of the study each subject will be categorized as having had one or more serious adverse events, or not having had any serious adverse events.

Statistical Methods:

Primary Outcomes:

For each outcome, repeated measures analysis of variance (RMANOVA), where post-operative pain control method (bolus block, continuous catheter) is the between subjects effect and post-operative day is the within subjects effect will be used to examine the association between pain control method and that outcome. Site (stratification variable) will be included as a covariate in each model. The interaction of post-operative control method and day will be included in the model. If the interaction is significant, then pairwise comparisons of pain control method at each day will be carried out within the RMANOVA model. If the usual assumptions required for the ANOVA model are not met, then a suitable transformation, or an appropriate non-parametric method will be used.

Secondary Outcomes:

For binary outcomes measured on days 1,2,3,4,7 and 10:

For each outcome, a generalized linear mixed model (GLMM) for binary clustered (i.e., hierarchical) data will be used to examine the association between pain control method and that outcome. GLMM will be used to account for the hierarchical structure of the data, (namely, multiple days within a subject). Site (stratification variable) will be included as a covariate in each model.

For binary outcomes measured on day 10 only:

For each outcome, logistic regression will be used to examine the association between pain control method and that outcome. Site (stratification variable) will be included as a covariate in each model.

For satisfaction with surgery:

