Analysis of variance (ANOVA) will be used to examine the association between pain control method and satisfaction with surgery. Site will be included as a covariate in the model. If the usual assumptions required for the ANOVA model are not met, then a suitable transformation, or an appropriate non-parametric method will be used.

Sample Size Justification:

In a published study of 85 patients undergoing arthroscopic shoulder surgery, patients were randomly assigned to catheter (43 patients) or single-shot block (42 patients) for postoperative analgesia. Median pain with movement on day 3, measured on a visual analog pain scale, 6 in the single-shot group and 4 in the catheter group. As there is limited information available regarding postoperative pain levels following ACL reconstruction, we will assume that the difference in pain levels between bolus block and continuous catheter will be similar (i.e. continuous catheter will be 2 points lower than bolus block). The standard deviation will be estimated as 2.5. This estimate was obtained by dividing the range (10-0) by 4.

The proposed analysis will examine pain levels over multiple days during the postoperative period. If a significant interaction between treatment and day is found, it will be of interest to determine which days differ. Although this comparison will be carried out within the ANOVA model, the 2 sided two sample t-test will be used for purposes of calculating the required sample size. A sample size of 39 subjects per group will yield 80% power to detect a 2 point difference between the two groups on any single day using a two sided two-sample t-test at the 0.01 significance level. The reason for applying this “Bonferroni-type” adjustment is that pairwise comparisons will be carried out for 6 different days, and with this number of statistical tests, it is more likely to find a significant difference at the nominal 5% level when one does not actually exist. Based on our experience, most, if not all patients return for the postoperative visit, and therefore, no adjustment for drop-out has been made. Therefore, the proposed sample size will be 78 subjects (39 for each treatment group). |

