 - a. This is a rare complication that is usually transient and goes away with time. The estimated incidence is .5% for any nerve irritation after the procedure. The risk of injury to the nerve that is permanent in 1/10,000. These are very rare in part due to the implementation and success of ultrasound use for guidance of the needle and/or catheter during nerve blockade. This allows the anesthesiologist direct visualization to differentiate between perineural, intraneural, and interfascicular.
 - b. These injuries will be monitored with a physical examination after the procedure once the patient has woken from anesthesia. Any deficits beyond what is expected by the nerve blockade will be followed at post-operative visit in the office to evaluate for resolution of transient symptoms. In the event of a peripheral nerve injury there is no intervention that can change the outcome of the block that has been delivered. If symptoms fail to progressively improve, neurological consultation should be sought in 3-4 weeks. Incomplete lesions with evidence of moderate or severe deficit are an indication for early neurological consultation and consideration of neurophysiologic testing (nerve conduction studies and electromyography).
2. Local Anesthetic System Toxicity
 - a. Ranges from mild symptoms of metallic taste, agitation, and circumoral numbness to more severe findings such as seizure, respiratory arrest, cardiac arrhythmias.
 - b. Manifestations of local anesthetic toxicity typically appear 1 to 5 minutes after the injection, but onset may range from 30 seconds to as long as 60 minutes. These symptoms will be monitored for and usually happen because of accidental injection into the vascular system. This is exceedingly rare with the advent of ultrasound

guidance and direct visualization of the injection. During the procedure the patients are attached to full monitors which will monitor blood pressure, cardiac rhythm, oxygen saturation. Any noticeable severe findings are treated with supportive care with propofol, lipid infusions which can reverse the effects from the local anesthesia.

- c. Lipid infusion protocol as recommended by the ASEA practice advisory on local anesthetic systemic toxicity is as follows:

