1. Both anesthetists and surgeons recognize the benefits of peripheral nerve catheters (PNCs). The continuous infusion of local anesthetic near a peripheral nerve or plexus produces fewer systemic side-effects than i.v. opioids, increases postoperative patient satisfaction, and can allow for faster functional recovery of the operated limb.
2. Block Failure
 - a. Occasionally, there are instances when the catheter is passed easily but the nerve block fails to provide adequate anesthesia or analgesia.
 - b. This is rare with the use of ultrasound guidance and localization of the continuous catheter.
 - c. In the event of a block failure or inadequate placement that is not providing the patient any relief, the catheter will be removed either by the patient or post operatively depending on when it is discovered.
 - d. The practicing anesthesiologist will discuss with the patient the option of either trying a second time to place the catheter successfully in the post anesthesia recovery area or discontinuing the block altogether.
3. Accidental Catheter Migration/Removal
 - a. The incidence of accidental catheter removal is reported in the literature at about 1%. The use of sterile adhesive tagaderm dressing has been implemented to firmly secure the catheter to the skin to avoid migration or fall out. The dressing is checked to be secure after it has been applied.
 - b. In the event that the catheter is accidentally removed or dislodged during the course of the study, it should be removed and there will be no further intervention once the patient has been discharged home. The patient can place a Band-Aid over the catheter site and notify the coinvestigator or PI.
4. Localized Infection
 - a. Localized inflammation is infrequent (0–10%), and local infection (0–3%), abscess formation (0–0.9%), and sepsis occur even more rarely.
 - b. Transparent dressings are used to reduce the number of dressing changes while appropriately monitoring the site for signs of inflammation
 - c. Since the continuous catheter remains in for 48-72 hours, it does pose a theoretical increased risk of infection compared to a single shot adductor canal block although this has not been proven in the literature. To minimize this risk the site is prepped in sterile fashion with either chlorhexidine or iodine scrub. The injecting physician washes hands and uses sterile gloves and instruments for the course of this procedure.

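### Serious adverse events are to be compared by logistic regression with no fallback, although one arm of 39 will more likely than not have none at assumed rates of 0.5% to 3%

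*Combined protocol and SAP*

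**What the plan says.** Section 12 (Secondary Outcomes) lists adverse events and serious adverse events among the outcomes of the post-operative follow-up visit. Each is reduced to one yes/no value per subject. They are the only binary outcomes in that list, so the Statistical Methods rule for binary outcomes measured on day 10 only applies to them: "For each outcome, logistic regression will be used to examine the association between pain control method and that outcome". The next sentence adds: "Site (stratification variable) will be included as a covariate in each model". Randomization is stratified by five hospitals, so site is a five-level factor. On allocation: "Subjects will be randomly assigned in a 1:1 ratio to either bolus block or continuous catheter". The sample size is 78, or 39 per arm.

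The two ANOVA-type methods in the same section each have a fallback (a transformation or a non-parametric method) if assumptions fail. The logistic model has none.

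Section 16, repeated in Section 17, gives risks for single components only. For the single-shot block: "The estimated incidence is .5% for any nerve irritation after the procedure", with permanent nerve injury at 1 in 10,000. For the catheter: "Localized inflammation is infrequent (0–10%), and local infection (0–3%), abscess formation (0–0.9%), and sepsis occur even more rarely", plus accidental removal at about 1%. No rate is given for any SAE or for any adverse event as a whole.

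**The concern.** An ordinary logistic model cannot estimate a treatment odds ratio when one arm has no events: the likelihood keeps rising as the coefficient goes to infinity. Software then stops at an arbitrary large value with a huge standard error, and the Wald p-value drifts towards 1 whatever the other arm shows. With 39 per arm and rare events, an empty arm is an ordinary result.

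Two things are at stake. First, the default output can read as no difference when the table shows a clear excess in one arm. The catheter stays in place for 48-72 hours, partly at home, and several listed harms can occur only with a catheter, so an empty bolus arm beside a non-empty catheter arm is plausible. Second, the trial is open-label and the plan names no substitute, so the replacement method would be chosen after the events by arm are known.

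**Working it through.** **Plan's own figure.** The documents give no figure for the safety analysis. The sample size they do give reproduces: for a 2-point difference, SD 2.5 and 80% power, "using a two sided two-sample t-test at the 0.01 significance level" requires 38.19 per group, rounded up to 39 (power at 39 is 81.0%). So n = 39 per arm is used below.

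**SAE rate (assumption).** No SAE rate is stated. I take a common rate p of 0.5% to 3% per arm, spanning the 0.5% for nerve irritation and the 3% upper figure for local infection. Not every such event would be serious, so this range is not low for SAEs.

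**Chance of an empty arm.** Let q = (1 − p)^39 be the chance that one arm has no event. Then P(both arms empty) = q², P(exactly one empty) = 2q(1 − q), and P(at least one empty) = 1 − (1 − q)².

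| p per arm | q | both empty | exactly one empty | at least one empty |
|---|---|---|---|---|
| 0.5% | 0.822 | 68% | 29% | 97% |
| 1% | 0.676 | 46% | 44% | 89% |
| 2% | 0.455 | 21% | 50% | 70% |
| 3% | 0.305 | 9% | 42% | 52% |
| 5% | 0.135 | 2% | 23% | 25% |
| 10% | 0.016 | 0.03% | 3% | 3% |

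In the last column the treatment odds ratio is infinite, zero or undefined. The figure falls below one half at p of about 3.1%. Simulation of 200,000 trials per scenario, applying the finiteness condition for the site-adjusted model, agrees at the rates in the table: 97%, 89%, 70%, 52%, 25% and 3%. It hardly changes between equal hospitals and an assumed uneven 40/16/10/8/4 split.

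**Unequal arms.** With bolus rate b and catheter rate c, P = (1 − b)^39 + (1 − c)^39 − (1 − b)^39(1 − c)^39. For b = 0.5% and c = 3%: 0.822 + 0.305 − 0.822 × 0.305 = 0.877, or 88%.

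**What the model prints.** Take 0/39 bolus and 8/39 catheter, with the events spread over five near-equal hospitals. The site-adjusted fit gives a treatment standard error of about 12,600 and a Wald p of 0.999. Fisher's exact test on the same table gives p = 0.005. This table illustrates the mechanism; 8/39 is 20.5%, far above the assumed SAE rates.

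**Role of the hospitals.** Take near-equal hospitals, events in both arms, and two hospitals with none. The treatment log-odds ratio is 0.843 (SE 0.922) with those hospitals in the model, and the same with them removed. Only their own coefficients diverge. An empty hospital therefore adds nothing to the treatment comparison but does not break it.

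**The case against.** Four points can be made for the plan.

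- **The text says logistic regression, not maximum likelihood with a Wald test.** This is correct. A likelihood-ratio test remains usable with one empty arm: for 0/39 versus 8/39, ignoring site, 2 × {[8 ln(8/39) + 31 ln(31/39)] − [8 ln(8/78) + 70 ln(70/78)]} = 2 × (−19.79 + 25.79) = 12.0 on 1 df, p about 0.0005. Firth estimation would also fit the wording. But the plan names neither, and ordinary software reports the maximum-likelihood estimate with a Wald test. A likelihood-ratio test also leaves the odds ratio itself infinite.
- **Safety is only a listed secondary outcome.** It is absent from the objectives table, the specific aim and the hypotheses. This limits the weight of the point but does not remove it.
- **An exact test would rarely be significant.** Fisher's test needs 6 versus 0 for p < 0.05 (5 versus 0 gives 0.055). At a 3% rate, the chance of 6 or more events among 39, Σ C(39,k) 0.03^k 0.97^(39−k) over k ≥ 6, is about 0.1%. This stands: the gain is a reportable estimate and interval, not power.
- **Component risks are not an overall rate.** This also stands, which is why the SAE rates above are assumptions shown over a range.

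A reader might infer two stronger things. One is that the five-hospital covariate is what makes the model fail. The check above shows otherwise: at a 10% event rate in both arms, some hospital coefficient diverges in 66% of trials (equal hospitals) to 90% (assumed uneven), but the treatment estimate fails in only 3%. The other is that the any-adverse-event model will usually fail too. The documents do not support that: Section 16 gives an open-ended list that includes block failure, site pain, allergy and pump failure without rates, and Section 11 counts any deterioration as an adverse event. The overall rate may well be high enough for the model to work.

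**Conclusion.** The point holds for serious adverse events. The specified analysis has no finite maximum-likelihood treatment estimate in 52% to 97% of trials for SAE rates from 3% down to 0.5% per arm, and no fallback is given. This rests on 39 analysed per arm and on those assumed rates; above about 3.1% per arm, failure is no longer the more likely result. It does not depend on hospital sizes or on having site in the model.

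For any adverse event the plan has a gap, not a likely failure: 25% of trials at 5% per arm and 3% at 10%, with the true rate unknown. The change should be made before outcome data by arm are examined.

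**What to change.** In Section 12, take the two safety outcomes out of the general rule for day-10 binary outcomes and state:

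- **Serious adverse events:** number and percentage of subjects by arm; the risk difference (catheter minus bolus) with an exact 95% confidence interval, naming the interval procedure; and a two-sided Fisher's exact test. No logistic model.
- **Any adverse event:** logistic regression on pain control method and site, fitted by Firth's penalized likelihood, with a penalized-likelihood-ratio test and profile penalized-likelihood 95% confidence interval, whatever the event count.

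Each outcome then has one method, fixed in advance, that gives a result even when an arm or a hospital has no events. The change is to wording only and needs no further patients, visits or data. Its price is that the SAE comparison is no longer adjusted for site and will have little power at these rates, so the report should rest on the counts and interval and should not read a large p-value as evidence of equal safety.

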4. OBJECTIVE(S)/SPECIFIC AIMS AND HYPOTHESES

- *A concise statement of the goal(s) of the current study.*
- *The rationale for and specific objectives of the study.*
- *The goals and the hypothesis to be tested should be stated.*

OBJECTIVES	ENDPOINTS	JUSTIFICATION FOR ENDPOINTS
Primary		
To Compare the efficacy of two different modes of administration of peripheral nerve block for postoperative pain control after primary ACL reconstruction.	Pain control as measured by a visual analogue scale (0-10) on post operative day 1,2,3,4,7, and at first follow up visit (Day 14).	Our study seeks to better clarify the effectiveness of two postoperative pain control methods after ACL reconstruction. Visual analogue scale is commonly used to assess pain in postoperative patients. This is an easy way to assess patients pain in a quick and easy to understand method.
Secondary		
To compare the daily opioid consumption in patients post operatively after ACL Reconstruction.	This will be measured as daily consumption of oxycodone (morphine equivalents) on post operative day 1,2,3,4,7, and 14.	A secondary objective of our study would be to examine pain control objectively by opioid consumption each day. This is a secondary measure of the efficacy of pain control. The hope is that with better pain control via peripheral nerve block patients would be less reliant on opioid pain medication.
To determine the effectiveness of pain control and quality of sleep.	We will measure this by asking if they had a disturbance in their sleep or trouble getting to sleep through email surveys.	Our study wants to look at how pain control and sleep quality are correlated and to analyze if better pain control also allowed patients to have better postoperative sleep habits.

General Well Being	Short Form - 12 Survey given preoperatively and at 14 days post operatively.	This assessment test is to classify changes in general health and wellbeing, physical, and mental health.
Knee Assessment Score	International Knee Documentation Committee Subjective Knee Form (IKDC) to be given preoperatively and at 14 days post operatively.	Designed to assess patients with a variety of knee disorders.

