- d. Perioperative antibiotics will also be given which is standard protocol for ACL reconstruction regardless of catheter insertion or not.
- e. In the event that the patient notices any skin irritation, redness, foul smell, or drainage from the site of the injection, they will be advised to first call the safety officer, PI, or other co-investigator to describe their symptoms. The patients will also watch for fevers or chills. If infection is suspected they will be sent to the emergency room or surgeon's office for evaluation and further testing. They may be started on a course of oral antibiotics if an infection is concerning after evaluation

5. Local Anesthetic System Toxicity

- a. The patients with a continuous catheter will be receiving a fixed rate of flow of local anesthetic to the nerve site for 48-72 hours. This does put them at a theoretical risk for toxicity while they are at home with the catheter in even though the dosage is well below the threshold for systemic toxicity. They will be educated on the following signs and symptoms similar to the single shot patients.
- b. Ranges from mild symptoms of metallic taste, agitation, and circumoral numbness to more severe findings such as seizure, respiratory arrest, cardiac arrhythmias.
- c. Manifestations of local anesthetic toxicity typically appear 1 to 5 minutes after the injection, but onset may range from 30 seconds to as long as 60 minutes. These symptoms will be monitored for and usually happen because of accidental injection into the vascular system. This is exceedingly rare with the advent of ultrasound guidance and direct visualization of the injection. During the procedure the patients are attached to full monitors which will monitor blood pressure, cardiac rhythm, oxygen saturation. Any noticeable severe findings are treated with supportive care with propofol, lipid infusions which can reverse the effects from the local anesthesia.
- d. Lipid infusion protocol as recommended by the ASEA practice advisory on local anesthetic systemic toxicity is as follows:
 - i. 1.5 ml kg⁻¹ bolus of 20% lipid emulsion Infusion at 0.25 ml kg⁻¹ per min for at least 10 min after return of circulatory stability Consider giving a second bolus and increasing infusion to 0.50 ml kg⁻¹ if circulatory stability not attained Upper limit of lipid emulsion recommended is 10 ml kg⁻¹ over the first 30 min.

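### The 80% power for any single day is right for a stand-alone t-test at 0.01, but it ignores the interaction test that must be passed first; the 0.01 is absent from Statistical Methods, and six test days elsewhere are seven in the outcome list

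*Combined protocol and SAP*

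**What the plan says.** All references are to Section 12 unless stated.

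- **Sample Size Justification.** The trial is sized so that "39 subjects per group will yield 80% power to detect a 2 point difference between the two groups on any single day". The difference is 2 points and the SD 2.5, and the power was worked out "using a two sided two-sample t-test at the 0.01 significance level". The paragraph names the interaction condition ("If a significant interaction between treatment and day is found, it will be of interest to determine which days differ") and says that the t-test serves for sizing only. The 0.01 is explained as a Bonferroni-type allowance because "pairwise comparisons will be carried out for 6 different days".
- **Statistical Methods, Primary Outcomes.** "If the interaction is significant, then pairwise comparisons of pain control method at each day will be carried out within the RMANOVA model". No level is given here for the interaction or for the day comparisons.
- **Primary Outcome list.** "Outcomes measured on post-operative days 0, 1,2,3,4,7, and at the post-operative follow-up visit": seven times.
- **Section 4, objectives table.** Pain is assessed by "visual analogue scale (0-10) on post operative day 1,2,3,4,7, and at first follow up visit (Day 14"): six times, without day 0.
- **Section 16, toxicity risks of the catheter.** Catheter patients will be "receiving a fixed rate of flow of local anesthetic to the nerve site for 48-72 hours". This is the document's only indication of how the benefit might be spread over days.

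**The concern.** The sizing test and the planned procedure are not the same. The sizing test always looks at the day in question. The planned procedure looks at it only if the two arms' profiles over time are shown not to be parallel. The chance of passing that first step depends on how much the benefit varies between days, not on how large it is on the day of interest. The Sample Size Justification assumes a 2-point difference and gives no pattern over days, so nothing in it limits the 80% to the patterns where it holds.

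Two smaller gaps go with this. An analyst working from Statistical Methods alone has no level for the day tests and could reasonably use 0.05. And the allowance for multiple testing is built on six days while the outcome list has seven.

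At stake is whether the trial can say on which days the catheter helps, and with what error rate.

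**Working it through.** **1. The plan's own figure.** Inputs from the Sample Size Justification: difference 2, SD 2.5, n = 39 per arm, two-sided 0.01. Standardised difference = 2/2.5 = 0.8. Noncentrality = 0.8 × √(39/2) = 3.53 on 2 × 39 − 2 = 76 df; the critical value is 2.64. Noncentral-t power is **81.0%**; with 38 per arm it is 79.8%. The stated figure reproduces, and 39 is the minimum.

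**2. The same test at exact Bonferroni levels, 39 per arm.** At 0.05/6 = 0.0083, power is 79.2% (40 per arm for 80%). At 0.05/7 = 0.0071, it is 77.6% (41 per arm for 80%).

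**3. Adding the gate.** Assumptions not in the document: interaction tested at 0.05; compound symmetry with within-patient correlation ρ from 0.3 to 0.7; SD 2.5 on every day; no site effect or missing data; the effect shapes below. With K = 6 days and day effects δ, the interaction F test has 5 and 76 × 5 = 380 df and noncentrality

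λ = (n/2) × Σ(δ − mean δ)² / [SD² × (1 − ρ)] = 19.5 × SS / [6.25 × (1 − ρ)] = 3.12 × SS / (1 − ρ).

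For example, 2,2,2,1,1,1 has mean 1.5 and SS = 6 × 0.25 = 1.5, so λ runs from 3.12 × 1.5/0.7 = 6.7 to 3.12 × 1.5/0.3 = 15.6. The gate column comes from the noncentral F distribution. The last column is simulated (20,000 to 40,000 trials per setting for most shapes): the gate opens and day 3 is significant at 0.01.

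| Effect on days 1, 2, 3, 4, 7, visit | SS | Gate opens | Day 3 tested and significant |
|---|---|---|---|
| 0,0,2,0,0,0 | 3.33 | 86-100% | 75-81% |
| 2,2,2,0,0,0 | 6.00 | 99-100% | about 81% |
| 2,2,2,1,0.5,0 | 3.875 | 91-100% | 75-81% |
| 2,2,2,1.5,1,0.5 | 2.00 | 61-96% | 52-78% |
| 2,2,2,1,1,1 | 1.50 | 47-88% | 41-72% |
| 2,2,2,1.5,1.5,1.5 | 0.375 | 14-28% | 11-24% |
| constant 2 | 0 | 5% | about 4% |

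Day 3 carries the same 2 points in every row. Without the gate, Bonferroni for six days gives 79% in every row. Holm gives 79% if only day 3 differs and 87-89% for a constant 2.

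**4. Level of the day tests.** Under the gate with six days, if any day truly differs, at most 5 are null, so 0.01 is defensible: 5 × 0.01 = 0.05. With seven days the bound is 6 × 0.01 = 0.06; the simulated rate of at least one false day is 4.0-5.2% when only day 3 differs. If 0.05 is used after the gate instead, that rate is **15-22%** (six or seven days, only day 3 differing), because the real day-3 effect usually opens the gate.

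**5. Count of times.** Section 4: 1, 2, 3, 4, 7, visit = 6. Sample Size Justification: 6. Primary Outcome list: 0, 1, 2, 3, 4, 7, visit = 7. Statistical Methods says only that each day is compared.

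**The case against.** The case for leaving the text alone is substantial. The paragraph labels its 80% as the power of a t-test at 0.01, says that the t-test is for sizing only, and mentions the interaction. Sizing on a simpler test is ordinary practice. The 0.01 and its reason stand in the same section as the methods. The infusion length favours an early, uneven benefit, for which the stated power roughly holds; the poor rows need benefit that lasts well after the catheter is out. A constant 2 points would be found by the treatment main effect with 98-100% power, and over all the shapes in the table except 2,2,2,1.5,1.5,1.5, for which this was not computed, the main effect or the gated day-3 test detects benefit in 78-100% of trials. Day 0 may be collected without being compared.

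Most of this stands and limits the point. A reader might infer that the power calculation is wrong, that the trial is too small, or that it would miss a real benefit. The document supports none of these: the arithmetic reproduces, N need not change, and overall detection is largely preserved. Nor is it right that the day level is never stated; it is stated once, as a sizing input.

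What does not fall away is this. Naming the gate is not the same as allowing for it. The main effect cannot say which days differ, which is the question the trial was sized on. And the section that governs the analysis gives no level and leaves open whether each day includes day 0.

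**Conclusion.** The point holds in a limited form, and its severity is minor to moderate. The 80% is a correct figure for one ungated t-test, but it is not the power of the planned procedure for any single day. Under the assumptions in the working, the procedure roughly delivers it when benefit is confined to the infusion period or fades quickly afterwards. It falls well short when benefit persists, down to about 4% when benefit is constant. No single range covers the persisting shapes, so each figure should be read only with its own shape.

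The results depend on an interaction level, a correlation structure and effect shapes that the document does not give. Compound symmetry matters: with a first-order autoregressive correlation of 0.7, the gate opens in about 8% of null trials instead of 5%. All error rates are for one outcome and do not cover the three listed as primary (maximum pain, current pain, opioid use).

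The missing level is the more practical risk: 15-22% false-day error if 0.05 is used after the gate and only day 3 differs. The six-or-seven discrepancy is real but numerically small.

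**What to change.** N stays at 78.

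(a) In Statistical Methods, report the treatment difference with its confidence interval at every time, whatever the interaction shows, and test the times by Holm or Bonferroni at two-sided 0.05 within each outcome. Both parts are needed: dropping the gate and testing six days at an unadjusted 0.05 gives 17-24% false-day error when no day differs. State that this control is within an outcome and does not extend across the three primary outcomes.

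(b) Reconcile six times (Section 4, Sample Size Justification) with seven (Primary Outcome list), and say whether day 0 belongs to the test family.

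(c) Restate single-day power at 39 per arm as 79% (six times, 0.0083) or 78% (seven times, 0.0071). Holm gives at least this.

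If the sponsor prefers to keep the gate, write the interaction level and the day level into Statistical Methods: 0.01 for six times, or 0.05/6 = 0.0083 for seven (6 × 0.0083 = 0.05). Add that the power figure is for the day test alone and ignores the gate.

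Cost: a few sentences, and a stated power 1-2 points lower. Visits and data collection do not change.
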